5.3. End-of-Study Analysis

The end of study analysis will include unblinded efficacy, safety and immunogenicity data. For secondary endpoints #2, #3 and #4, formal inference as part of the testing strategy will occur during this analysis.

Note: The timing of the end-of-study analysis is based on last subject last visit of the global cohort but will include all participants of global and local cohorts enrolled up to the cut-off of the final analysis.

6. STATISTICAL ANALYSES

6.1. General Considerations

6.1.1. Study Phases

A baseline (or reference) value for safety (except from vital signs) and immunogenicity will be defined as the value of the last available assessment prior to vaccination on Day 1. If no immunogenicity assessment was performed pre-vaccination, the (first) post-vaccination assessment on Day 1 will be used as the baseline value for the immunogenicity analysis, if available.

A baseline (or reference) value for all efficacy analysis, except from vital signs for the whole study will be defined as the value of the available assessment at Day 1 visit, if Day 1 visit is not available the Day 1 unscheduled visit closest to the day of vaccination will be used. In case two or more assessments are available at the same visit or at the same day of the selected baseline visit the worst will be used (per question).

For vital signs, the vital sign assessment collected at the pre dose timepoint will be defined as baseline (or reference).

For all efficacy analysis 'Month 12' will be defined similar to Day 1. 'Month 12' will be defined as the value of the available assessment at 'Month 12' visit, if 'Month 12' visit is not available the 'Month 12' unscheduled visit closest to the relative day 365 will be used. In case two or more assessments are available at the same visit or at the same day of the selected 'Month 12' visit the worst will be used (per question).

The safety analysis will present all results by phase. Immunogenicity results will be presented per scheduled time point as appropriate. Listings will be shown per phase/period and time point. Efficacy results will be presented across the first year, second year, whole study or per timepoint, where appropriate.

Study day or relative day is defined as follows:

Study Day = visit date – date of Day 1 + 1; if visit date \geq date of Day 1 (date of vaccination).

Study Day = visit date – date of Day 1; if visit date $<$ date of Day 1 (date of vaccination).

6.1.2. Phase Definitions

The phases in the study will be constructed as follows:

Table 4: Phase Definitions

Phase	Phase #	Period	Period #	Interval	
				From	To
Screening	1			Date and time of signing the informed consent form	One minute prior to start of post dose period
Regimen	2	Post-Dose	1	Date and time of vaccination	Minimum of:

Table 4: Phase Definitions

Phase	Phase #	Period	Period #	Interval	
				From	To
					a) 23:59 at the date of last contact (for early study discontinuation) b) 23:59 at the database cut-off date in case of interim analysis c) Maximum (28 days after vaccination at 23:59, scheduled visit 4 weeks after vaccination at 23:59)
First Year Follow up	3			One minute after Post-Dose period end	Minimum of: a) 23:59 at the date of last contact (for early study discontinuation) b) 23:59 at the database cut-off date in case of interim analysis c) One minute prior to Second Year Follow up
Second Year Follow up	4			00:00 at the date of the Month 12 visit *	Minimum of: a) 23:59 at the date of last contact (for early discontinuation or participants that completed the study) b) 23:59 at the database cut-off date for analyses conducted before the final analysis.

The combination of 'Post-Dose' period and 'First Year Follow up' period will be referred as 'First Year'. The combination of the 'Regimen', 'First Year Follow up' and 'Second Year Follow up' periods will be referred as 'Whole Study' phase.

*If Month 12 visit not available, and there are ARI surveillance questions available after the relative day 365, then the relative day 365 (vaccination date + 365) will be used as the start of the Second Year Follow up.

'Month 12' and 'Day 365' visit are used interchangeably in the rest of the document.

For the potential adverse events of special interest (AESI) analysis the following intervals will also be used:

Table 5: Interval Definition for potential AESI analysis

Dose	Interval	Interval	
		From	To
Post-vaccination	0 - 28 days post-dose	Date time of vaccination	Min of: 
 • 23:59 at date of last contact (for discontinuations) • 23:59 at the database cut-off date in case of interim analysis • Maximum (date of vaccination + 28 days at 23:59, date of scheduled visit 4 weeks after vaccination at 23:59)
	29 - 56 days post-dose*	One minute after the end of the interval '0 - 28 days post-dose'	Min of: 
 • 23:59 at date of last contact (for discontinuations)

			
 • 23:59 at the database cut-off date in case of interim analysis • Date of vaccination + 56 days, at 23:59
	57 days - 6 months post-dose	One minute after the end of the interval '29 - 56 days post-dose'	Min of: 
 • 23:59 at date of last contact (for discontinuations) • 23:59 at the database cut-off date in case of interim analysis • Maximum (Date of vaccination + 169 days at 23:59 , date of scheduled visit 169 days post vaccination at 23:59)
	> 6 months post-dose	One minute after the end of the interval '0 - 6 months post-dose'	Min of: 
 • 23:59 at the date of last contact (for discontinuations/ completions) • 23:59 at the date of DB cut-off for interim analyses

The combination of the '0 - 28 days post-dose' interval and the '29 - 56 days post-dose' interval will be referred as '0 - 56 days post-dose'. The combination of the '0 - 28 days post-dose', '29 - 56 days post-dose' and '57 days - 6 months post-dose' intervals will be referred as '0-6 months post-dose'.

*In case the '0 - 28 days post-dose' interval end later than 56 days post vaccination then the '29 - 56 days post-dose' interval is not required.

For example, if a participant had Day 29 visit at relative day 57, then the following intervals will be created:

- 0 - 28 days post-dose, lasting from 0 to relative day 57,
- 57 days - 6 months post-dose, lasting from 58 onwards.

The same logic will apply for all intervals that end later after the next interval.

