
 • To demonstrate the efficacy of active study vaccine in the prevention of RT-PCR-confirmed RSV-mediated LRTD during the second year when compared to placebo in adults aged 60 years and above 	
 • First occurrence of RT-PCR-confirmed RSV-mediated LRTD during the second year, with onset after study Day 365

 • To demonstrate the efficacy of active study vaccine in the prevention of any RT-PCR-confirmed RSV-mediated ARI during the second year when compared to placebo 	
 • First occurrence of any RT-PCR-confirmed RSV-mediated ARI during the second year, with onset after study Day 365

Objectives	Endpoints

 To demonstrate the efficacy of active study vaccine in the prevention of predefined clinically relevant disease associated with RT-PCR-confirmed RSV-mediated ARI over the whole study when compared to placebo 	
 First occurrence of predefined clinically relevant disease associated with RT-PCR-confirmed RSV-mediated ARI over the whole study with onset at least 14 days after dosing of study vaccine
NON-CONFIRMATORY SECONDARY	

 To evaluate safety in terms of serious adverse events (SAEs) and adverse events of special interest (AESIs) until 6 months after vaccination 	
 Occurrence and relationship of vaccination to SAEs and AESIs until 6 months after vaccination

 In the Safety Subset and in subgroups of the Safety Subset (including but not limited to participants at increased risk of severe RSV disease), to evaluate the safety and reactogenicity in terms of solicited local and systemic adverse events (AEs) during 7 days after vaccination, and in terms of unsolicited AEs during 28 days after vaccination 	
 Occurrence, intensity, duration and relationship to vaccination of solicited local and systemic AEs during 7 days after vaccination and of unsolicited AEs during 28 days after vaccination

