Humoral immunity sample, mL	● ^x 20	● ^x 20		● 20	● 20		● ^x 20	● ^x 20	
Cellular immunity sample, mL	● 40	● 40		● 40	● 40		● 40	● 40	
Nasosorption sample (SAM)	●	●					●		
SAFETY SUBSET ONLY:									
Thermometer training and distribution	●								
Ruler training and distribution	●								
Solicited AE recording ^y	●								
Unsolicited AE recording ^z	Continuous								
Concomitant medications	Continuous								
Vital signs ^{aa}	● ●								
eDiary review of solicited AEs by study staff		●							
Blood Draw Volumes: IMMUNO SUBSET PARTICIPANTS									
Approx. daily blood draw, mL	62	62		60	60		62	60	
Approx. cumulative blood draw, mL	62	124	124	184	244	244	306	366	366
Blood Draw Volumes: NON-IMMUNO SUBSET PARTICIPANTS									
Approx. daily blood draw, mL	17	17					17		
Approx. cumulative blood draw, mL	17	34	34	34	34	34	51	51	51

1 pre-dose

Note: At any clinic visit, an abbreviated, symptom directed physical examination may be performed if deemed necessary by the investigator based on any clinically relevant issues, clinically relevant symptoms, and medical history.

Footnotes:

- a. For Immuno Subset participants, where the timing of the 24-week post-vaccination visits and end of first RSV season or Month 6 (Day 182) visits may overlap, procedures can be combined.
- b. For the Northern Hemisphere (NH), the end of the first RSV season is defined as 15 April 2022. For the Southern Hemisphere (SH), the end of the first RSV season is defined as 30 September 2022. This visit (Visit 3) is then referred to as “End of first RSV season” visit. End of first RSV season procedures may be conducted on the same day as Visit 1, or before Visits 2, 2a, 2b, and 2c depending on the date of enrollment of the participant. If a participant is enrolled after the maximum window of the “End of first RSV season” visit (ie, after 29 Apr 2022 for NH and after 14 Oct 2022 for SH), only a “Month 6” (182 days, -7/+14 days post vaccination) safety follow-up call is required to collect information on SAEs and potential AESIs.

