- n. Participants will be randomized at Day 1 in a 2:1 ratio to receive active vaccine (Group 1) or placebo (Group 2) (see Section 6.3).
- o. The RiiQ, EQ-5D-5L, and the PGI-H will be completed by the participant in the eDiary. The questionnaires need to be completed at the “End of first RSV season” visit but not at the Month 6 (Day 182) follow-up.
- p. Participants may use their own eDevice (or desktop computer, where applicable) using a study-specific application instead if their device (smartphone or tablet) is compatible. eDevices provided to the participant should be returned to the site at the end of the study.
- q. Participants will be re-trained on how to use the eDiary, if needed, and on how to collect a nasal swab. Participants will be provided with 2 nasal swab kits.
- r. All participants will be closely observed for a minimum of 15 minutes post-vaccination to monitor for the development of any acute reactogenicity. This post-vaccination observation period should be extended for participants whom in the investigator’s opinion would require further observation or for any occurrence of a localized reaction or (minor) systemic symptoms during the post-vaccination observation that require monitoring for any progression.
- s. All (S)AEs and special reporting situations related to study procedures or to non-investigational (concomitant) Janssen products will be collected from ICF signature onwards until the end of the study for all participants. All other SAEs will be collected from administration of study vaccine (Day 1) until 6 months after vaccination. AEs leading to discontinuation from the study will be collected for the duration of the study.
- t. AESIs, including potential AESIs, are to be reported to the sponsor within 24 hours of awareness from the moment of vaccination until 6 months after vaccination (See Section 8.5.6).
- u. All COVID-19 cases will be collected for all participants for the duration of the study. COVID-19 cases reported by the participant to the investigator and any ARI positive for SARS-CoV-2 will be reported in the eCRF by the investigator.
- v. Concomitant medications will be collected for all participants for the duration of the study when associated with any SAEs and AESIs and/or with any AEs leading to discontinuation from the study.

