The Immuno Subset should contain at least 180 participants from North America, at least 180 from Europe, and ~120 from each of the other regions in the setting that these are part of the study. In each region, ~50% of the Immuno Subset will be at increased risk of severe RSV disease and ~50% will be 75 years or older.

No other caps are installed for the Global cohort.

In each of the regions, the non-increased risk Safety Subset must be fully enrolled before further enrollment of non-increased risk participants. Also, the 60-74 years Safety Subset must be fully enrolled before further enrollment of participants aged 60-74 years. Similarly, in each region, the increased risk Safety Subset must be fully enrolled before further enrollment of increased risk participants. Also, the 75-years-and-older Safety Subset must be fully enrolled before further enrollment of participants aged 75 years and older. Immuno Subset participants will be enrolled only at a selection of sites.

Additional local cohort enrollment, beyond the Global cohort enrollment, may be allowed if required by local health authorities for the purpose of local regulatory approval consideration. This will also be handled via the IWRS and will follow the same randomization ratio as the Global cohort. Stratification and minimization will be done in a similar way as for the Global cohort. The number of 60-64 year old participants in those local cohorts will be a maximum 10% of the total cohort. Caps for the Immuno Subset and the Safety Subset will depend on local requirements.

Blinding

The investigator will not be provided with randomization codes. The codes will be maintained within the IWRS, which has the functionality to allow the investigator to break the blind for an individual participant.

In general, for the Global cohort, randomization codes will be disclosed fully only if the study is completed and the clinical database is closed. The participants, study site personnel (except for those with primary responsibility for study vaccine preparation and dispensing), and investigator will be blinded to the study vaccine allocation until the end of the study. The sponsor will be blinded to Day 1 study vaccine allocation until the database lock for the primary efficacy analysis except for the sponsor representatives involved in independent drug monitoring.

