The timings of post-vaccination visits will be determined relative to the actual day of vaccination.

The following visit windows will be allowed as indicated:

Visit #	Visit Day/ Visit Week	Visit Window	Primary Purpose
2	15/ 2	+3 days	2 weeks after vaccination, Safety and Immuno visit
2a ^a	29/ 4	+3 days	4 weeks after vaccination, Safety visit by telephone or telemedicine contact
2b ^b	85/ 12	±7 days	12 weeks after vaccination, Immuno visit
2c ^b	169/ 24	±14 days	24 weeks after vaccination, Immuno visit
3 ^c	182/"End of first RSV season"/26	-7/+14 days	26 weeks after vaccination (Month 6)/End of season 1 assessments. Safety and efficacy visit
4	365/ 52	-7/+14 days	52 weeks after vaccination (Month 12). Safety and Immuno visit
4a ^b	533/ 76	±14 days	76 weeks after vaccination. Immuno visit
5	730// 104	-7/+14 days	104 weeks after vaccination (Month 24) assessments. Follow-up visit

a. Safety Subset only.

b. Immuno Subset only.

c. Please refer to the [Schedule of Activities](#) for the exact timing of visits and assessments to be performed.

Sample Collection and Handling

The actual dates and times of sample collection for the immunogenicity assessments must be recorded in the eCRF or laboratory requisition form.

Refer to the [Schedule of Activities](#) for the timing and frequency of all sample collections.

Instructions for the collection, handling, storage, and shipment of the samples can be found in the Laboratory Manual that will be provided. Collection, handling, storage, and shipment of the samples must be under the specified, and where applicable, controlled temperature conditions as indicated in the Laboratory Manual.

Study-Specific Materials

The investigator will be provided with the following supplies:

- Investigator's Brochure for Ad26/protein preF RSV vaccine
- Site Investigational Product Procedures Manual
- Investigational Product Preparation Instruction
- Laboratory Manual
- IWRS Manual
- Electronic Data Capture (eDC) Manual/eCRF completion guidelines
- Sample ICF
- ePRO completion guides
- ePRO participant information sheets
- eDiaries and instructions for use
- Rulers (to measure diameter of any erythema and swelling)
- Thermometers
- Nasal swab sample kits, including cooling bags
- RT-PCR machines and supplies for performing respiratory panel tests
- Pulse oximeters
- Laboratory kits
- Contact information page(s)

[figure not shown]

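### SAP Table 5 closes its six-month safety interval at study Day 170, 12 days before the protocol's Month 6 (Day 182)

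*SAP*

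**What the plan says.** SAP 6.1.2, Table 5, defines post-vaccination intervals for potential AESIs. Leaving aside last contact and database cut-off, the interval from 57 days to 6 months closes at the later of two dates: vaccination plus 169 days, or the "date of scheduled visit 169 days post vaccination at 23:59". The interval for more than 6 months opens one minute later. SAP 6.1.1 counts days as "Study Day = visit date – date of Day 1 + 1".

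The protocol keeps the 24-week and Month 6 visits apart. In the visit-window table of Section 8, Visit 2c (Day 169, ±14 days) is "24 weeks after vaccination, Immuno visit" and is restricted to the Immuno Subset. Visit 3 (Day 182, -7/+14 days) is "26 weeks after vaccination (Month 6)/End of season 1 assessments. Safety and efficacy visit".

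Footnote t of Section 1.3.1 has AESIs reported "from the moment of vaccination until 6 months after vaccination", and other SAEs follow the same six-month period. The matching secondary endpoint in the Synopsis is "Occurrence and relationship of vaccination to SAEs and AESIs until 6 months after vaccination".

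SAP 6.7.1.1.2 presents all potential AESI analyses by these intervals, and SAP 6.10.2 adds SAE analyses by the same intervals. SAP 6.11, written after the study was terminated, presents safety in the final analysis only by the Table 4 periods.

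**The concern.** The six-month limit appears to have been tied to the 24-week immunogenicity visit instead of the Month 6 safety contact. If so, events from the last 12 days of the protocol's six-month period are reported in the wrong column.

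The later column suffers as well. After 6 months, SAE collection narrows, mainly to events related to study procedures or concomitant sponsor products and to serious RSV, hMPV or influenza infections. Under Table 5 that column would mix 12 days of full collection with a long stretch of restricted collection.

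Table 4 breaks only at about 28 days and at Month 12. Table 5 therefore holds the only SAP interval labelled 6 months, and a reader looking for the six-month safety result would naturally turn to it.

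The visit term also makes the boundary depend on subset membership and on how late a blood-draw visit happened to be.

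**Working it through.** **Day convention.** Study day = date − vaccination date + 1 (SAP 6.1.1). Check against the Schedule of Activities: vaccination + 28 gives Day 29, and vaccination + 168 (24 weeks) gives Day 169. Both agree with the schedule.

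**Table 5 limit.** Vaccination + 169 gives 169 + 1 = study Day 170. This matches neither the Day 169 visit nor Day 182.

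**Protocol Month 6.** 26 weeks × 7 = 182, which reproduces the stated Day 182. The window is 182 − 7 = Day 175 to 182 + 14 = Day 196, so the Table 5 limit lies before the whole window.

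**Gap.** 182 − 170 = 12 days (Days 171 to 182), and 12/182 = 6.6%. Footnote b of protocol 1.3.1 speaks of 182 days post vaccination. Read literally, that is study Day 183, and the gap is 13 days (13/183 = 7.1%).

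**Effect of the visit term.** Visit 2c may fall between 169 − 14 = Day 155 and 169 + 14 = Day 183.

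| Visit 2c | Interval ends | Days up to 182 placed after 6 months |
|---|---|---|
| none, or by Day 170 | Day 170 | 12 |
| Day 175 | Day 175 | 7 |
| Day 183 | Day 183 | 0 |

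**Who has no Visit 2c.** Protocol 6.3 plans at least 180 Immuno Subset participants from North America and at least 180 from Europe, and about "120 from each of the other regions in the setting that these are part of the study". With 360 of 23,000, 1 − 360/23,000 = 98.4% have no Visit 2c. Adding 120 from the Southern Hemisphere gives 1 − 480/23,000 = 97.9%. The 180s are minimum sizes, so the percentage is approximate.

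**Share of events.** The documents give no SAE or AESI rates. Let k be the hazard on Days 171 to 182 relative to Days 1 to 170 (an assumption). The share of six-month events placed in the later column is 12k/(170 + 12k):

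- k = 0.5: 6/176 = 3.4%
- k = 1: 12/182 = 6.6%
- k = 2: 24/194 = 12.4%

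**The case against.** The best reply is that little turns on this. SAP 6.11 says the full planned analysis will not be done after termination and confines final safety output to Table 4 periods, which can be read as overriding the by-interval tables. Table 5 is supplementary and is nowhere named as the analysis of the secondary safety endpoint. SAEs and potential AESIs are also tabulated over the whole study (SAP 6.7.1.1.1), both arms follow the same rule, and nothing is formally tested. These limits on the consequence stand.

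Section 6.11 does not settle the matter, however. Section 6.10 and its by-interval SAE tables came in with the same SAP version 4.0, dated after the termination, and neither section mentions the other. A programmer cannot tell which instruction governs.

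It can also be said that Month 6 is a visit target with a window and not a sharp limit, and that events are allocated by onset date, so the date of the Month 6 call does not matter for allocation. Both remarks are correct. Neither rescues Day 170, which precedes every date the protocol associates with Month 6.

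Finally, dropping the visit term departs from the day-or-visit rule that Tables 4 and 5 also use at 28 days. There, the visit named matches the interval's label. At six months it does not, and the protocol offers no suitable replacement visit.

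**Conclusion.** The concern holds. As written, Table 5 places onsets on Days 171 to 182 after 6 months for about 98% of participants, and for some of the rest in part or not at all, depending on their Visit 2c date. The mislabelled period is 12 of 182 days (6.6%), or 13 of 183 if Month 6 means 182 days after vaccination. Any statement about the share of events rests on an assumed hazard.

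This is an allocation error in descriptive tables. No event is lost from the Table 4 or whole-study summaries. Thrombosis with thrombocytopenia syndrome is the least affected event, because protocol 2.2 puts its onset at about 1 to 2 weeks after vaccination. The correction should be made, but it does not affect the efficacy conclusions.

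**What to change.** In Table 5, replace both the 169-day term and the Day 169 visit term with one fixed boundary for every participant at the protocol's Month 6 day, 182, keeping the last-contact and cut-off terms. State the convention: study Day 182 is vaccination + 181 days under SAP 6.1.1, whereas 182 days after vaccination is study Day 183.

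The Visit 3 date should not be used in its place. It is set by the calendar: footnote b of protocol 1.3.1 allows that "End of first RSV season procedures may be conducted on the same day as Visit 1". Under footnote c it can also fall well after 6 months with no separate Day 182 call.

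Add one sentence to SAP 6.10.2 or 6.11 saying whether by-interval SAE and AESI tables belong to the final analysis. Any 0 to 6 month table that is produced should use the corrected boundary.

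The cost is one table entry, one sentence, and a re-run of the by-interval tables if they are produced.
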